Grade 3 thrombocytopenia without bleeding	Any	Withhold AZD4573 until Grade \leq 2 or baseline level. Restart AZD4573 at the same dose level.
Grade 4 thrombocytopenia without bleeding requiring blood or platelet transfusion	First occurrence	Withhold AZD4573 until Grade \leq 2 or baseline level. Restart AZD4573 at the same dose level.
	Second occurrence	Withhold AZD4573 until Grade \leq 2 or baseline level. Restart AZD4573 with 1 level dose reduction. If not recovered to Grade \leq 2 or baseline level discontinue.
	Third occurrence	Discontinue AZD4573.
Grade 3 or 4 thrombocytopenia with bleeding requiring blood or platelet transfusion	First occurrence	Withhold AZD4573 until Grade \leq 2 or baseline level. Restart AZD4573 with 1 level dose reduction. If not recovered to Grade \leq 2 or baseline level discontinue.
	Second occurrence	Discontinue AZD4573.

^a Adverse reactions are graded using NCI CTCAE version 5.0.

^b In cases where more than 21 days are needed, a decision to continue, modify, or discontinue study treatment will be made on a case-by-case basis in consultation with the principal investigator and the Study Physician.

Abbreviations: ANC, absolute neutrophil count; ASCO, American Society of Clinical Oncology; ESMO, European Society for Medical Oncology; G-CSF, granulocyte-colony stimulating factor.

Dose modifications for AZD4573 for abnormal liver chemistry test results are described in [Table 12](#).

Table 12 Recommended Dose Modifications for AZD4573 for Abnormal Liver Chemistry Test Results

Event ^a	Action
Isolated^b elevations in ALT, AST, or bilirubin	
Grade 1 Isolated ALT/AST \leq 3 \times ULN or Isolated Bilirubin \leq 1.5 \times ULN	Maintain current dose level. Monitor ALT, AST, ALP, and bilirubin at least 1x per week.

Event ^a	Action
Grade 2 Isolated ALT/AST > 3 to $\leq 5 \times$ ULN or Isolated Bilirubin > 1.5 to $\leq 3 \times$ ULN	After 7 days if hepatic enzymes resolve to Grade ≤ 1 , re-challenge at same dose level.
Grade 3 Isolated ALT/AST > 5 to $20 \times$ ULN	If recovered to Grade ≤ 1 within 7 days, allow re-challenge at same dose level. If not recovered to baseline level within 7 days, discontinue AZD4573.
Grade 3 Isolated Bilirubin > 3 to $10 \times$ ULN	If recovered to baseline level within 96 hours (-2/+12 hours) of start of dose allow re-challenge at same dose level. If not, discontinue AZD4573.
Grade 4 Isolated ALT > $20 \times$ ULN or Isolated Bilirubin > $10 \times$ ULN	Discontinue AZD4573.

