Grade 4 Isolated elevation ($\geq 20 \times$ ULN) in AST without concomitant elevation in ALT $\geq 20 \times$ ULN or concomitant elevation in TBL $\geq 2 \times$ ULN that fails to return to baseline level within 7 days from start of dosing	Discontinue AZD4573.
Grade 4^c Isolated AST elevation $\geq 20 \times$ ULN without concomitant elevation in ALT $\geq 20 \times$ ULN or TBL $\geq 2 \times$ ULN	First occurrence If recovered to Grade ≤ 1 or baseline level within 7 days of start of dose allow re-challenge at same dose level.
	Second occurrence If recovered to Grade ≤ 1 or baseline level within 7 days of start of dose allow re-challenge with 1 dose level reduction.
	Third occurrence Discontinue AZD4573.
Concurrent elevations in ALT, AST, or bilirubin (Please also refer to the HL appendix in the CSP for actions to be taken in the event of PHL)	
ALT or AST $\geq 3 \times$ ULN with TBL $\geq 2 \times$ ULN (PHL) AND INR $\geq 1.5 \times$ ULN (or $\geq 1.5 \times$ baseline if elevated at baseline) of any duration	Discontinue AZD4573.

Event ^a	Action
ALT or AST $\geq 3 \times$ ULN with the appearance of fatigue, nausea, vomiting, right upper quadrant pain or tenderness, fever, rash, and/or eosinophilia $> 5\%$	Discontinue AZD4573.
ALT or AST $\geq 3 \times$ ULN and TBL $\geq 2 \times$ ULN where TBL does not return to baseline level within 96 hours (-2/+12 hours) from start of dose and/or AST or ALT do not return to baseline level within 7 days from start of dose	Discontinue AZD4573.
Grade 3 elevation ($\geq 5 \times$ ULN) in ALT or AST with TBL elevation above baseline level or ULN, but $< 2 \times$ ULN that do not return to baseline level within 7 days	Discontinue AZD4573.
ALT and AST $\geq 3 \times$ ULN with concomitant TBL $\geq 2 \times$ ULN, NO increase in INR $\geq 1.5 \times$ ULN (or 1.5 \times baseline), and NO fatigue, nausea, vomiting, right upper quadrant pain or tenderness, fever, rash, and/or eosinophilia $> 5\%$	If recovered to Grade ≤ 1 or baseline level within 96 (-2/+12) hours, re-challenge at same dose level ^c .

^a Adverse reactions are graded using NCI CTCAE version 5.0.

^b Elevations in ALT or AST are considered isolated if bilirubin remains below Grade 1, and elevations in bilirubin are considered isolated if ALT and AST remain below Grade 1.

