10.6.2.1.3 Management of Hydration

Adequate fluid intake for all participants enrolled into the study is mandatory, in particular, around the times of AZD4573 dosing.

All participants are **mandated** to receive IV fluid hydration with normal saline (NaCl 0.9%). For participants at intermediate or high risk for TLS (per Table 13), normal saline 500 mL should be administered over 2 to 4 hours prior to AZD4573 and then continued at a rate of 100 to 175 mL/hr as tolerated to maintain urine output at least until the 6 hour TLS monitoring lab assessment, and thereafter if medically indicated.

In case of diarrhoea/nausea/vomiting, more aggressive IV fluid hydration may be needed as clinically indicated. Participants are also encouraged to drink enough fluid before and after each dosing. Please use diuretics carefully; do not use them prophylactically, only if participants have signs of hyper-hydration.

10.6.2.2 Transaminases Increase With or Without Concomitant Bilirubin Increase and the Risk of Liver Injury

Transaminase elevations are an important identified risk for participants treated with AZD4573. Evidence of abnormal liver function should be monitored as per the protocol guidelines. Increased levels of AST, ALT, or serum bilirubin should trigger an investigation of the cause, which may include viral infection or disease progression with liver infiltration. The investigator should consider whether the abnormal liver chemistry test results meet the criteria for expedited reporting.

Bilirubin increase with transaminase increase (ALT or AST or both) is included as an important identified risk for AZD4573. Biochemical changes of increased transaminases with concomitant increase in bilirubin fulfilling criteria for potential Hy's law have been observed in participants treated with AZD4573. These events resolved rapidly and have to date not been associated with any adverse clinical sequelae or lasting liver damage. Upon re-challenge with AZD4573, there is no consistent pattern of recurrence, nor is there any consistent increase in severity of the events. As such, whilst the events follow the biochemical definition of Hy's law, the clinical pattern is rapidly self-limiting and does not seem to predict any lasting liver damage.

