Liver injury is classified as an important potential risk for AZD4573. Participants who experience increases in transaminases or bilirubin levels after AZD4573 dosing must be monitored in line with Section 10.8.2.5. Please refer to Section 10.6.1 (dose modification and re-treatment) for additional information on how to manage a participant with increases in transaminases/bilirubin.

Additional **CCI** [REDACTED] will also be collected for central analysis (see Section 10.8.9.3).

If bilirubin fails to resolve within 96 (-2/+12) hours or transaminases fail to resolve within 7 days, or if the event is associated with significant clotting abnormality or clinical symptoms of liver disease, study treatment must be permanently discontinued (the participant remains on study for the 30-day Follow-up and LTFU visits), and the event must be immediately communicated to AstraZeneca.

For guidance on treating liver toxicity, please refer to Section 10.6.2, Table 12.

During the course of the study the investigator will remain vigilant for increases in liver

biochemistry. The investigator is responsible for determining whether a participant meets PHL criteria at any point during the study.

[Appendix E](#) describes the process to be followed to identify and appropriately report cases of PHL. It is not intended to be a comprehensive guide to the management of elevated liver biochemistries.

The investigator will participate, together with the Study Physician, in review and assessment of cases meeting PHL criteria to agree whether HL criteria are met.

The investigator is responsible for recording data pertaining to PHL/HL cases and for reporting AEs and SAEs according to the outcome of the review and assessment in line with standard safety reporting processes.

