10.6.3 Criteria for Restarting Treatment

The criteria to be met before a participant receives further study drug infusions following a pause in treatment, either within 1 cycle or between cycles, is as below:

All participants:

- 1 Participant has recovered from all treatment-related non-haematological toxicity to CTCAE Grade ≤ 2 .
- 2 Recovery of neutrophils $> 1000/\mu\text{L}$ and platelets $> 75000/\mu\text{L}$ or $> 50000/\mu\text{L}$ with bone marrow involvement.
- 3 Participant has recovered from all hepatic toxicity events within the timeframes described in Table 12 above. If biochemical changes in transaminase(s) and total bilirubin are consistent with the definition of HL, the participant may continue to receive study drug only if all abnormalities have resolved within the timeframes specified in Table 5 above, there are no symptoms of liver injury and INR has not increased above $1.5 \times \text{ULN}$ (or $1.5 \times \text{baseline}$). In these circumstances the participant must be made aware of the unknown potential for liver damage with continued exposure to AZD4573 prior to retreatment. Documentation of continued consent is required.

- 4 Recovery of uric acid to < ULN.
- 5 Recovery of changes in uric acid, potassium, phosphorus, creatinine or calcium, or symptoms suggestive of TLS as defined in [Table 11](#).

10.7 Discontinuation of Study Intervention and Participant Discontinuation/Withdrawal – Module 1

See the SoA (Section [10.1.2](#)) for data to be collected at the time of intervention discontinuation and follow-up and any further evaluations that need to be completed.

Please refer to Section [7](#) (Core protocol) for information on discontinuation of study intervention and participant discontinuation/withdrawal.

10.8 Study Assessments and Procedures – Module 1

- Study procedures and their timing are summarised or linked to in the SoA. Protocol waivers or exemptions are not allowed.
- Immediate safety concerns should be discussed with the sponsor immediately upon occurrence or awareness to determine if the participant should continue or discontinue study intervention.
- Adherence to the study design requirements, including those specified in the SoA, is essential and required for study conduct.

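### Table 12 gives opposite instructions, with no stated precedence, for a symptomatic rise in both ALT and AST with bilirubin below Grade 1

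*Protocol*

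**What the plan says.** Protocol Section 10.6.1, Table 12, has two blocks: isolated elevations, and concurrent elevations in ALT, AST or bilirubin.

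- **What counts as isolated (footnote b).** "Elevations in ALT or AST are considered isolated if bilirubin remains below Grade 1". The test for a transaminase rise is bilirubin alone. ALT and AST raised together still count as isolated, and symptoms play no part.
- **Isolated ALT/AST rows.** Grade 1 (up to 3 × ULN): "Maintain current dose level. Monitor ALT, AST, ALP, and bilirubin at least 1x per week". Grade 2 (above 3 to 5 × ULN): "After 7 days if hepatic enzymes resolve to Grade" 1 or lower, re-challenge at the same dose. Grade 3 (above 5 to 20 × ULN): re-challenge if recovered within 7 days. Grade 4 AST without ALT at or above 20 × ULN: re-challenge on the first occurrence at the same dose and on the second one level lower, if recovered within 7 days; discontinue on the third. Grade 4 ALT: discontinue.
- **Symptom row, in the concurrent block.** ALT or AST at least 3 × ULN "with the appearance of fatigue, nausea, vomiting, right upper quadrant pain or tenderness", fever, rash and/or eosinophilia above 5%: discontinue. It is the only one of the five rows in that block without a total bilirubin condition.
- **Last row of the concurrent block.** This re-challenge row, for both enzymes with raised bilirubin, does exclude symptoms: "and NO fatigue, nausea, vomiting, right upper quadrant pain or tenderness" and the rest of the list.

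Section 10.6.2.2, headed "Transaminases Increase With or Without Concomitant Bilirubin Increase and the Risk of Liver Injury", adds that if bilirubin or transaminases do not resolve in time, "or if the event is associated with significant clotting abnormality or clinical symptoms of liver disease, study treatment must be permanently discontinued". Section 10.6.3, item 3, requires that "there are no symptoms of liver injury and INR has not increased above" its limit, but only where the changes fit Hy's law.

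**The concern.** Take a participant with ALT 4 × ULN, AST 4.5 × ULN, normal bilirubin and INR, and nausea, with both enzymes back at baseline by Day 7. The isolated Grade 2 row re-challenges at the same dose. The symptom row discontinues. Neither the table, its footnotes nor the text of Section 10.6.1 ranks them.

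The two actions are opposite and one cannot be undone: under Section 7.1 a participant whose treatment is stopped for safety may not restart it. A site that follows the symptom row may permanently stop someone for ordinary drug-related nausea alongside a transient enzyme rise. A site that reads only the isolated row may overlook the Section 10.6.2.2 stop. Different sites can handle the same case differently.

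**Working it through.** The plan gives no figure to reproduce. The check sets each row against one case: ALT and AST both at least 3 × ULN, bilirubin below Grade 1, normal INR, one listed symptom, first occurrence.

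**Step 1. Which rows apply.** The symptom row's enzyme and symptom conditions are met in every such case. Its block heading can be read to cover ALT raised together with AST. By footnote b, the isolated rows apply as well.

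**Step 2. Grade pairs above the 3 × ULN boundary.** Take 4, 10 and 25 × ULN to represent Grades 2, 3 and 4. This gives 3 × 3 = 9 pairs. The symptom row says discontinue in all nine. The isolated rows say:

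| | AST Grade 2 | AST Grade 3 | AST Grade 4 |
|---|---|---|---|
| ALT Grade 2 | re-challenge if recovered | re-challenge if recovered | re-challenge if recovered |
| ALT Grade 3 | re-challenge if recovered | re-challenge if recovered | re-challenge if recovered |
| ALT Grade 4 | discontinue | discontinue | discontinue |

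Conflicts: 2 ALT grades × 3 AST grades = 6 of 9. Without recovery there is no conflict: the Grade 3 and Grade 4 AST rows then discontinue, and Section 10.6.2.2 requires a stop when transaminases do not resolve within 7 days. At a third Grade 4 AST occurrence the two AST Grade 4 cells in the upper rows also become discontinue, leaving 6 − 2 = 4 of 9.

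**Step 3. The boundary.** Counting exactly 3 × ULN as a fourth level gives 4 × 4 = 16 pairs and 3 × 4 = 12 conflicts. Of those, 12 − 6 = 6 need at least one enzyme at exactly 3 × ULN. The Grade 1 maintain instruction is the opposing one in only one pair, with both enzymes exactly at 3 × ULN.

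**Step 4. Search for a precedence rule.**

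| Place | What it settles | What it leaves open |
|---|---|---|
| Section 10.6.2.2 | Permanent stop for clinical symptoms of liver disease, with or without raised bilirubin | Does not define the term or link it to the Table 12 list; refers back to Table 12 for liver toxicity |
| Section 10.6.3, item 3 | No symptoms of liver injury, for Hy's law changes | Symptom condition does not reach bilirubin below Grade 1 |
| Section 6.6 | Study Physician discussion before dosing resumes | Which row governs |
| Section 8 | Immediate safety concerns go to the sponsor | Which row governs |
| Section 8.3.7 | Discontinuation discussions to be documented | Which row governs |
| Table 12, footnote c | Documented risk discussion before re-challenge after Grade 4 transaminase rises | Which row governs |

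None of the isolated maintain or re-challenge entries for ALT/AST (Grade 1, Grade 2, Grade 3, Grade 4 AST first and second occurrence: 0 of 5) carries a symptom condition.

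**The case against.** The strongest defence is that the two blocks exclude each other. Footnote b makes any rise with bilirubin below Grade 1 isolated, four of the five concurrent rows state a bilirubin condition, and the concurrent heading points to the Hy's law appendix. On that reading the isolated row governs the example, and the mandatory wording of Section 10.6.2.2 overrides a table that is titled as recommendations and, for Grade 3 and Grade 4 AST, only allows re-challenge. Whether the nausea comes from the liver is then ordinary clinical judgement. Alternatively, an investigator could take the symptom row as the more specific and more cautious one.

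Much of this stands. A reader might infer that no reading of the table works. That is too strong: the exclusive-blocks reading combined with Section 10.6.2.2 gives a usable answer. A reader might also infer that participants with liver symptoms would be re-dosed unsupervised. The documents do not support that: Section 10.6.2.2 requires the stop and Section 6.6 puts the Study Physician before any resumption.

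What does not go away is that the protocol never says which reading it intends. The symptom row carries no bilirubin condition, unlike the other four rows in its block, and its heading fits ALT with AST. Both readings are reasonable, and they give opposite actions for a non-specific listed symptom.

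**Conclusion.** The inconsistency is in the printed text and should be corrected. With both enzymes raised, bilirubin below Grade 1 and a listed symptom, Table 12 both allows re-challenge after recovery and says discontinue. The size is 6 of 9 grade pairs above the 3 × ULN boundary, at a first or second Grade 4 AST occurrence where that grade applies, and only if the enzymes recover. This rests on reading footnote b literally and on the concurrent heading including ALT with AST.

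The unresolved part is narrow: which row governs, and whether a non-specific symptom such as nausea counts. Symptoms of liver disease are already decided by Section 10.6.2.2.

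Two larger figures may tempt a reader. The count of 12 of 16 takes half its conflicts from pairs with an enzyme at exactly 3 × ULN, so it overstates the overlap. Section 10.6.2.4 reports nausea and vomiting in about half of dosed participants, but that is not how often they coincide with a rise in both enzymes at normal bilirubin. The documents give no joint frequency, so no rate of affected participants is claimed.

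**What to change.** (a) Add to the isolated ALT/AST maintain and re-challenge rows (Grade 1, Grade 2, Grade 3, Grade 4 AST first and second occurrence): *provided there are no clinical symptoms of liver disease (Section 10.6.2.2)*.

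(b) Add a footnote to the symptom row stating whether it applies when bilirubin is below Grade 1 and, if it does, that it takes precedence over the isolated rows.

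An exception for fatigue, nausea, vomiting or fever judged unrelated to the liver is for the sponsor to choose and is not part of the required fix; on one reading it would loosen a stop now printed without conditions. A blanket statement that the symptom row applies at every bilirubin level would also take in single-enzyme rises, so the sponsor should write that only if it is meant.

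The cost is minor wording, with no new visits or data. Depending on the choice in (b) there may be some additional discontinuations; the documents give no frequency from which to estimate them.

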^c Participants who are considered for re-challenge in the event of Grade 4 transaminase increases or PHL must discuss possible risk of hepatotoxicity with the treating physician, who will document this discussion and participant agreement for continued treatment in the medical records.

Adequate supportive therapy as per Institutional guidelines should be given for all toxicities.

Abbreviations: ALP, alkaline phosphatase; ALT, alanine aminotransferase; AST, aspartate aminotransferase; CTCAE, Common Terminology Criteria for Adverse Events; HL, Hy's Law; INR, international normalised ratio; PHL, Potential Hy's Law; TBL, total bilirubin; ULN, upper limit of normal.

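### Table 12 stops AZD4573 for an isolated Grade 4 ALT or bilirubin rise but permits the same dose when the same peak is part of a fast-recovering combined rise

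*Protocol*

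**What the plan says.** All rows are in Protocol Section 10.6.1, Table 12.

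- **Isolated Grade 4 ALT or bilirubin.** The row headed "Grade 4 Isolated ALT" (ALT above 20 x ULN, or isolated bilirubin above 10 x ULN) says discontinue, however fast the recovery.
- **Isolated Grade 4 AST** (20 x ULN or more, with ALT below 20 and TBL below 2 x ULN), recovering within 7 days. First occurrence: same dose. Second: "allow re-challenge with 1 dose level reduction". Third: discontinue.
- **Isolated Grade 3 ALT or AST.** On recovery "within 7 days, allow re-challenge at same dose level. If not recovered to baseline level within 7 days, discontinue AZD4573". There is no occurrence count.
- **Footnote b.** "Elevations in ALT or AST are considered isolated if bilirubin remains below Grade 1", and the converse holds for bilirubin.
- **Concurrent rises.** The stops depend on an INR rise, symptoms or slow recovery, for example "where TBL does not return to baseline level within 96 hours". The last row (ALT and AST at least 3 x ULN, TBL at least 2 x ULN, no INR rise, no listed symptoms) allows same-dose re-challenge on recovery to Grade 1 or lower "or baseline level within 96 (-2/+12) hours, re-challenge at same dose level".
- **Footnote c**, attached to that row. "Participants who are considered for re-challenge in the event of Grade 4 transaminase increases or PHL" must have a documented risk discussion and agreement.

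**The concern.** Under footnote b a potential Hy's Law event can never be isolated, so it cannot reach the Grade 4 ALT or bilirubin stop. The Grade 4 AST steps also exclude TBL of 2 x ULN or more. The event falls to the last concurrent row, which has lower bounds only.

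Two participants may therefore share an ALT peak above 20 x ULN and the same quick, symptom-free recovery. The one with normal bilirubin must stop, while the one with TBL of 2 x ULN or more may be re-dosed at the same level, repeatedly. Section 10.6.2.2 names the combined rise as an important identified risk and says that events meeting potential Hy's Law criteria have been seen. The written limits are thus looser for the pattern that the protocol singles out for special reporting.

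The concern covers only events with no listed symptoms, no INR rise and recovery within 96 (-2/+12) h. It does not dispute the sponsor's choice, explained in Section 10.6.2.2, to re-challenge after transient combined rises.

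**Working it through.** The protocol gives no figure to reproduce. The check applies Table 12 as written to matched pairs that differ only in bilirubin.

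**Inputs from Table 12.** Isolated stops at ALT > 20 and bilirubin > 10 x ULN; Grade 4 AST at >= 20 x ULN; concurrent re-challenge row at ALT and AST >= 3 with TBL >= 2 x ULN. The TBL limit with its tolerance is 96 + 12 = 108 h. The transaminase limit is 7 x 24 = 168 h.

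**Assumed cases.** Normal baseline, no symptoms, normal INR, all values back to baseline at the same hour. ALT 10 or 25, AST 10 or 25 (x ULN) and occurrence 1, 2 or 3 give 2 x 2 x 3 = 12 cells. Each compares normal TBL with TBL 3 x ULN.

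**Recovery at 90 h (within both limits), action at occurrences 1 / 2 / 3:**

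| ALT / AST | TBL normal | TBL 3 x ULN | Combined more lenient |
|---|---|---|---|
| 10 / 10 | same / same / same | same / same / same | 0 of 3 |
| 10 / 25 | same / one level lower / stop | same / same / same | 2 of 3 |
| 25 / 10 | stop / stop / stop | same / same / same | 3 of 3 |
| 25 / 25 | stop / stop / stop | same / same / same | 3 of 3 |

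More lenient: 0 + 2 + 3 + 3 = 8. Equal: 12 - 8 = 4. Stricter: 0. All 8 involve a Grade 4 transaminase.

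**Recovery at 140 h (past 108 h, within 168 h).** Every combined case stops. ALT 10/AST 10 moves from same dose to stop at all three occurrences (3 stricter). ALT 10/AST 25 is stricter at the first two and equal at the third (2 stricter). Both ALT 25 patterns stop either way (6 equal). Total: 0 more lenient, 7 equal, 5 stricter.

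**Recovery at 180 h.** All 12 stop in both columns.

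**Bilirubin pair, 90 h.** TBL 12 x ULN alone: stop. TBL 12 with ALT 5 and AST 5 x ULN: same dose at every occurrence.

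**Two uncovered patterns.** First, ALT 25 with TBL 1.6 x ULN matches no row at 90 h or 140 h. The only candidate, a Grade 3 elevation "in ALT or AST with TBL elevation above baseline level or ULN" but below 2 x ULN, acts only on failure to recover in 7 days, so the case stops at 180 h. Second, with TBL recovered at 90 h but transaminases at 140 h, neither concurrent row clearly applies, so this was not scored.

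**Do other sections supply the limit?** Table 11's third-occurrence stop for non-haematological toxicity excludes liver. Section 6.6 asks for Study Physician discussion before dosing resumes. Section 10.6.2.2 stops for slow recovery, clotting abnormality or symptoms. Section 10.6.3 requires timely resolution, no symptoms, no INR rise and continued consent. The cycle-start laboratory criteria test current values, not the earlier peak. Section 7.1.1 concerns pausing recruitment. Appendix E covers reporting and case review, including most repeat episodes, and refers management back to the Dose Modification section. None sets a peak or occurrence limit.

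**The case against.** **The scenario is narrow.** Nausea, vomiting, fever or fatigue with ALT or AST at 3 x ULN or more already means discontinue, and Section 10.6.2.4 reports nausea and vomiting in about half of participants. With a normal baseline, ALT 25 must fall to 3 x ULN or less (25/3 = 8.3-fold) within about 96 h. The visible Phase I text on Grade 4 rises (Section 10.4.2) concerns AST only. This stands, and it limits how often the gap would matter.

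**The count of 8 in 12 follows from the chosen inputs.** It does: 9 of the 12 cells contain a Grade 4 transaminase. The grid shows where the rows diverge; it is not a rate.

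**Review is heavy.** Every potential Hy's Law case is an SAE with expedited reporting (Section 8.3.7), restart presupposes clinical benefit (Section 10.6.1), and the investigator may stop at any time. This makes unreviewed re-dosing unlikely. It does not explain why the isolated peak has a fixed stop and the combined one does not.

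**The leniency may be deliberate.** Footnote c contemplates re-challenge after Grade 4 transaminase rises or potential Hy's Law events, and Sections 2.3.1 and 10.6.2.2 report benign re-challenge experience with combined events. The visible text does not say whether that experience included Grade 4 peaks, nor why an equally fast isolated ALT peak must stop.

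**Section 10.4.2 is weak support.** It describes Grade 4 AST rises lasting under 4 days and an expert view on isolated rises, but it concerns dose-limiting toxicity, is partly redacted and does not say how the duration was measured. This is fair, and the conclusion does not rest on it.

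**Conclusion.** The concern holds. For events with no listed symptoms, no INR rise and recovery within 96 (-2/+12) h, Table 12 is more permissive for a combined rise than for the same isolated peak in three situations: ALT above 20 x ULN, bilirubin above 10 x ULN, and a second or third AST of 20 x ULN or more. A first Grade 4 AST event and Grade 3-only rises are treated alike, and slower recovery is never handled more leniently in the combined block.

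The result follows from the row definitions and footnote b; the case values are illustrative. The visible documents do not say how often a Grade 4 peak occurs with TBL of at least 2 x ULN and recovers in time, so no frequency is claimed. Table 12 is headed as recommended and the row permits re-challenge without compelling it. This is a gap in the written limits that should be clarified, not a forced re-dose.

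**What to change.** Amend Table 12 as follows.

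1. Apply the discontinuation rules for ALT above 20 x ULN and bilirubin above 10 x ULN whether or not the other analyte is raised. This also covers ALT above 20 x ULN with TBL between 1 and 2 x ULN.
2. When AST is 20 x ULN or more, add occurrence steps to the concurrent re-challenge row at least as strict as the isolated ones (same dose, one level lower, discontinue). State whether isolated and combined events share one count.
3. Keep same-dose re-challenge for transient combined rises below Grade 4, and keep the 96 h and 7-day limits.

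With items 1 and 2 the 90 h grid becomes equal in all 12 cells: 8 combined cells change, 7 to discontinue and 1 to one level lower. The 140 h grid does not change. If the present difference is intended, the protocol should say why.

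The cost is a table correction in a protocol amendment, with no extra tests because every value is already collected. Some participants with transient combined Grade 4 rises would be reduced or stopped earlier.

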6.6 Dose Modification

If, in the opinion of the investigator, a participant experiences a clinically significant and/or unacceptable adverse reaction, then the dose may be temporarily or permanently halted or reduced.

Supportive therapy will be administered as required. Relevant reporting and discussion with the Study Physician will take place before resumption of dosing.

See the relevant module for detail on dose modification.

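### For liver events that resolve in time without symptoms or an INR rise, Table 12 stops an isolated extreme value but can allow a same-dose restart when a second liver test is also raised

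*Protocol*

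**What the plan says.** Table 12 in Protocol Section 10.6.1 has an isolated block and a concurrent block.

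- **Isolated, Grade 4.** ALT > 20 x ULN or bilirubin > 10 x ULN means discontinuation, whatever the recovery. Footnote b limits the block: "elevations in bilirubin are considered isolated if ALT and AST remain below Grade 1". ALT or AST rises count as isolated only while bilirubin is below Grade 1.
- **Isolated, Grade 4 AST.** AST >= 20 x ULN may be re-challenged after recovery within 7 days, provided it comes "without concomitant elevation in ALT" >= 20 x ULN or TBL >= 2 x ULN. The first occurrence restarts at the same dose. The second reads "or baseline level within 7 days of start of dose allow re-challenge with 1 dose level reduction". The third is a stop.
- **Concurrent, stops.** These need one of: INR >= 1.5 x ULN with PHL values; ALT or AST >= 3 x ULN "with the appearance of fatigue, nausea, vomiting, right upper quadrant pain or tenderness, fever, rash, and/or eosinophilia" > 5%; or failure to return to baseline in time.
- **Concurrent, last row.** ALT and AST >= 3 x ULN with TBL >= 2 x ULN, no INR rise and no symptoms: if recovered to Grade 1 or lower "or baseline level within 96 (-2/+12) hours, re-challenge at same dose level". The row states no upper value and no occurrence count.

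Table 11's one-level reduction after a Grade 4 non-haematological event excludes liver dysfunction, so it does not supply a restart dose.

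**The concern.** A dose-modification table should not become more lenient as the picture gets worse. Here the only stop triggered by a peak ALT or bilirubin value sits in the isolated block, and footnote b switches it off once the other test reaches Grade 1. The same ALT of 25 x ULN can then lead to a mandatory stop, no matching row, or a full-dose restart, depending on how far bilirubin rises.

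This bears on a risk the protocol takes seriously. Section 2.3.1 lists bilirubin increase with transaminase increase as an important identified risk, and Section 8.3.6 makes hepatotoxicity an event of special interest. Rapid resolution is how Section 10.6.2.2 describes the PHL changes seen so far, so the resolved branch is the relevant one. Table 6 also admits participants with ALT or AST up to 3 x ULN. Read on Table 12's own x ULN bands, someone dosed with ALT at 2 x ULN cannot have an isolated bilirubin rise while ALT stays there.

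**Working it through.** The plan has no figure to reproduce. The check applies Table 12 row by row.

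**Conditions.** Recovery to baseline within 96 hours, no symptoms, normal INR. Values are multiples of ULN.

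**Two readings of footnote b.** Literal: below Grade 1 means at or below ULN. Wide: isolated runs up to TBL < 2, or ALT and AST both < 3. The AST row's TBL qualifier suggests the wide reading, because under the literal footnote that qualifier is redundant.

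**Paired profiles, literal reading.**

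| ALT/AST/TBL | Result |
|---|---|
| 25/8/1 | stop |
| 25/8/1.3 | no row |
| 25/8/2.5 | same-dose re-challenge, no limit |
| 1/1/12 | stop |
| 2/2/12 | no row |
| 4/4/12 | same-dose re-challenge, no limit |
| 8/25/1 | AST row: reduce at second occurrence, stop at third |
| 8/25/1.3 | no row |
| 8/25/2.5 | same-dose re-challenge, no limit |

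**Grid.** ALT and AST each 1, 2, 4, 8 or 25; TBL 1, 1.3, 2.5, 5 or 12. This gives 5 x 5 x 5 = 125 profiles. Those with ALT > 20 or TBL > 10:
- ALT 25: 5 AST x 5 TBL = 25
- TBL 12 with ALT below 25: 4 x 5 = 20
- Total 45

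Literal reading:
- **Stop:** ALT 25 with TBL 1 (5), plus 1/1/12 (1) = **6**.
- **Last row, same dose:** ALT 25, AST 4, 8 or 25, TBL 2.5, 5 or 12 (9), plus ALT 4 or 8, AST 4, 8 or 25, TBL 12 (6) = **15**.
- **No row:** 45 - 6 - 15 = **24**. These are TBL 12 with ALT and AST below 3 but not both at 1 (3); ALT 25 with TBL 1.3 (5); and only one transaminase >= 3 with TBL >= 2 (16).

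On the wide reading the first two no-row groups (3 + 5 = 8) become stops: **14 stop, 15 same dose, 16 no row**. The 15 + 16 = 31 profiles that lose the stop on both readings all meet the PHL definition in Appendix E 2.

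**Grade 4 AST.** With AST 25, ALT 1, 2, 4 or 8 and TBL 2.5, 5 or 12 there are 4 x 3 = 12 profiles. Six (ALT 4 or 8) fall in the last row without an occurrence limit; six (ALT 1 or 2) match no row.

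**If unresolved.** Section 10.6.2.2 requires permanent discontinuation when bilirubin has not resolved by 96 hours or transaminases by 7 days. The gap is therefore confined to resolved events.

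**The case against.** **Restart after resolved PHL is intended.** Section 10.6.2.2 gives the reasons: quick resolution, no lasting damage, no consistent worsening on re-challenge. Footnote c provides for "Participants who are considered for re-challenge in the event of Grade 4 transaminase increases or PHL" and requires a documented risk discussion and agreement. Section 10.6.3, criterion 3, sets restart conditions. A reader might infer that such re-challenge is itself an error, or that 31 of 45 events would lose protection. The documents support neither: the policy is stated, and the 31 are unweighted cells, some of them unlikely (ALT 25, AST 1, TBL 12). The policy does not, however, explain why ALT of 25 x ULN alone is a mandatory stop while the same ALT with TBL of 2.5 x ULN is not. The readable expert review in Section 10.4.2 concerns isolated enzyme rises. Parts of that section are redacted and the Investigator's Brochure was not available.

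**No matching row is not no management.** A reader might infer that these participants are left unmanaged. They are not. Criterion 3 of Section 10.6.3 covers the 16 one-transaminase PHL profiles, lacking only a dose level. The general text of Section 10.6.1 requires interruption and/or reduction for Grade 3 or 4 toxicity, and clinical benefit before restart. Section 6.6 adds: "Relevant reporting and discussion with the Study Physician will take place before resumption of dosing". PHL is a mandatory SAE (Section 8.3.7) reviewed with the sponsor's physicians (Appendix E 5). Each new cycle requires the Table 6 limits to be met again (Section 10.1.2, footnote c). All of this stands, but none of it sets a stop by peak value.

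**The AST trade is not one-sided.** Once TBL reaches 2 x ULN the recovery clock tightens from 7 days to 96 hours, and INR rise and symptoms exclude re-challenge. That is a fair offset, but it does not replace an occurrence limit.

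**Symptoms may already stop many events.** Section 10.6.2.4 reports nausea and vomiting in about half of dosed participants, and either one with ALT or AST >= 3 x ULN is a stop. This limits how often the gap would matter.

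**Conclusion.** The point holds for liver events that resolve in time with no symptoms and no INR rise.

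- The Grade 4 ALT and bilirubin stop applies only to isolated rises. With ALT and AST >= 3 x ULN and TBL >= 2 x ULN, the same peak may be re-challenged at the same dose, with no ceiling and no occurrence limit.
- AST >= 20 x ULN loses its second-occurrence reduction and third-occurrence stop once TBL reaches 2 x ULN, in exchange for a shorter recovery clock.
- Non-PHL combinations (bilirubin > 10 x ULN with ALT or AST above ULN but both < 3 x ULN; ALT > 20 x ULN with TBL above ULN but < 2 x ULN) match no row on the literal footnote. They are 8 of the 45 cells, and their status depends on the reading.
- One-transaminase PHL has restart conditions but no stated dose.

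The counts assume that below Grade 1 means at or below ULN; the CTCAE text is not in the documents, so both readings are shown. They describe the table's logic. The documents give no frequencies, so the number of participants affected is unknown.

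**What to change.** 1. In footnote b, define isolated as not meeting any concurrent row. Where no concurrent row is met, apply the action for the higher-grade component, and the stricter action if two differ.
2. In the last concurrent row, exclude ALT > 20 x ULN and bilirubin > 10 x ULN from same-dose re-challenge, so that the existing Grade 4 stop applies whether or not the rise is isolated. All 45 grid profiles are then stopped.
3. Carry the Grade 4 AST sequence (same dose, one-level reduction, stop) into that row, and apply it to Grade 4 AST with TBL >= 2 x ULN when no concurrent row is met.

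If the sponsor's hepatic experts do intend restart above these values, the table should say so and give the dose and the occurrence limit. Changing the last row from ALT and AST to ALT or AST without the cap would make matters worse: 15 + 16 = 31 of the 45 profiles would qualify for same-dose restart.

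The cost is the wording of one footnote and one row, in an amendment needing IRB/IEC and regulatory approval (Appendix A 1). No tests or visits are added. A few participants who might have been re-challenged would stop.
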